The rhinology clinic at the University of Rochester Medical Center routinely follows CRS patients with nasal endoscopy and with disease-specific quality-of-life questionnaires. Our current clinical standard of practice includes obtaining a sinonal culture directed by nasal endoscopy and making treatment decisions based on the culture results. We will recruit post-ESS CRS patients with worsening symptoms and mucopurulence in the paranasal sinuses seen on nasal endoscopy. Up to 100 potential subjects meeting the defined inclusion criteria will be approached during routine clinic visits with a goal for enrollment of 70 patients. Enrollment is defined as entering the study and receiving treatment. We will screen more patients than will be enrolled, anticipating that approximately 30 patients will not be eligible for inclusion based on their culture results. Patients will not be eligible for inclusion if they are systemically ill at the time of their initial visit or if they require antibiotic treatment prior to finalization of culture data. Justification for a sample size of 70 (35 subjects per treatment group) is based on the assumptions that (1) 90% of patients taking culture-directed oral antibiotics will experience a clinical and statistically significant improvement in Rhinosinusitis Disability Index (RSID) score at the end of therapy, and (2) The non-inferiority limit of topical therapy is 20% of oral therapy. Using a standard deviation of 20% and a power of 0.9, 26 subjects will be required in each treatment group. We will enroll more subjects than required to compensate for any exclusions made once treatment is initiated and for subjects who drop out of the study.

Male and female adults of any race will be considered for inclusion. Mentally and physically disabled persons will be allowed to participate if they exhibit the capacity to consent to participate in the research, to carry out the treatment regimen, and to accurately communicate and record their symptoms, which will be based on the physician's assessment at their initial visit. There will be no exclusion based on economic or educational disadvantage. Prisoners will not be included in the study population due to difficulties coordinating care and administering nebulization therapy.

STUDY00000407

Version date: 03/07/2019

Inclusion criteria

1. Adults (age ≥ 18).
2. Diagnosis of CRS.
3. Worsening sinonasal symptoms.

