At the end of treatment, an otolaryngologist blinded to the treatment will repeat nasal endoscopy, cultures, and sinusal brushings to assess response. If there is no mucopurulent drainage within the sinusal cavity, 3 cc of normal saline will be irrigated into the maxillary sinus and sent for culture. Change in Rhinosinusitis Disability Index (RSDI) scores will serve as the primary outcome. The RSDI is a validated, rhinosinusitis-specific 30-item quality-of-life questionnaire.²⁵ It relates the physical, functional, and emotional quality-of-life domains to rhinosinusitis. The survey is set up as an equal-appearing five point scale designated by the words "never", "almost never", "sometimes", "almost always", and "always". Total scores range between 0 and 120 with high scores indicating greater burden of disease. Secondary outcomes will be change in Sinusal Outcome Test (SNOT)-22 scores,²⁶ change in nasal endoscopy findings using Perioperative Sinus Endoscopy (POSE) scores²⁷, post-treatment culture negativity defined as less than 1+ growth of organisms, and change in the total bacterial community following treatment as determined by RNA pyrosequencing. The study participants will be routinely followed in clinic with nasal endoscopy at 2 month intervals for

STUDY00000407

Version date: 03/07/2019

up to 6 months from the time of enrollment, or until the study is closed, to evaluate for disease recurrence or progression.

Molecular Analysis

For the molecular section of the study, samples will be collected via mucosal brushings and as detailed above in the Tami Sinus Secretion Collector. From the Collector, samples will be aseptically divided into two aliquots: one to the microbiology lab for conventional culturing, and one for molecular work. Each sample will be assigned a unique sample identification number (UID) that will be separated from the patient identification. This list will be administered by the study coordinator. Brushings and aliquots of the sample allocated to the molecular work will be transferred into lysis buffer for RNA pyrosequencing ²⁸. The remainder of the sample will be frozen, and maintained at -80C for the remainder of the study.

All of the collected samples of the study will be streaked for anaerobic growth in the research laboratory for speciation. The primary samples will then be analyzed for total bacterial 16s rRNA, allowing comparison of the microbiome within and between pre- and post-treatment in both study arms.

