It is anticipated that there may be patients that may not respond to the antibiotic treatment in either the oral or topical antibiotic treatment groups. In this case, the samples that were banked at -80C would be submitted for bacterial RNA transcriptional profiling. Additionally, the correlating banked nasal swab sample would be submitted for human RNA transcriptional profiling. This will allow comparison of the genes expressed by the bacteria that evaded antibiotic therapy in the two treatment arms. Similarly, it will also allow comparison of genes expressed by human endonasal mucosa in response to infection and therapy. Numbers of patients for this part of the study will be determined based on the failure of therapy rate.

After original patient samples have been speciated, and antibiotic sensitivity has been assessed, cultures from the Microbiology Lab will be given the correlating deidentified UID, and frozen at -80C to allow potential future analysis of the isolated strains. Study of these strains will be conducted using the deidentified UID. Samples will be kept at -80 for the remainder of the study.

Timeline

Time (Weeks)	Steps	Notes
Date of enrollment (Week 0)	
 1. Patient questionnaire completed in waiting room. 2. Patient examined with nasal endoscopy. 3. Cultures obtained. 4. Molecular analysis samples obtained and frozen. 5. Consent obtained. 6. Participant given sinus rinse bottle, and saline packets. 	
 • Part of current clinical practice. • Part of current clinical practice. • Part of current clinical practice.
Telephone call/Start of therapy (Day 3-7)	
 1. Antibiotic, placebo and nebulizer mailed to subject, or picked up by subject at the clinic, depending on the subject's preference. 2. Subject instructed on use of nebulizer. 3. Therapy initiated. 	
Telephone call (Start of therapy + 7 days)	
 1. Compliance check. 	
Follow-up (start of therapy +14 days)	
 1. Patient questionnaire completed in waiting room. 2. Patient examined with nasal endoscopy. 3. Cultures obtained 4. Molecular analysis samples obtained and frozen. 5. Therapy terminated. 	

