Routine follow-up (every 2 months)	
 1. Patient questionnaire completed in waiting room 2. Patient examined with nasal endoscopy. 	
 • Part of current clinical practice. • Part of current clinical practice.

Data Collection, Analysis and Monitoring

STUDY00000407

Version date: 03/07/2019

Data including patient demographics, endoscopic results, culture data, and quality of life questionnaire scores will be collected and stored on a password protected, encrypted share drive. Any printed data will be stored in the study personnel's office in a locked file cabinet. Only the study personnel will have access to identifying information. Research subjects will be given a unique study number that is stored separately from collected data. The results will be analyzed at the study's completion. A data safety monitoring plan will be ongoing and performed by the investigators. Any adverse events will be recorded and monitored for trends throughout the entire study period. Any serious adverse events will be scrutinized by the principal investigators and study termination will be considered if indicated.

Risk/Benefit Assessment

Risk Category

This is a greater than minimal risk study since it is not necessarily routine to repeat a nasal endoscopy and culture following completion of antibiotic treatment, particularly if the patient is symptomatically improved.

Potential Risk

Potential risks to the subject include mild discomfort and nasal irritation secondary to nasal endoscopy, in addition to any added inconvenience for having to return to the clinic for re-examination. There is a small risk of loss of privacy to the subjects. Genetic information obtained from human subjects will be limited to genes that are currently being expressed.

The remainder of the study is within accordance to the current standards of clinical practice and will not add any additional risk to the patients. The oral and topical treatments proposed are generally safe without any major adverse events reported in the literature.¹⁶ There are no anticipated benefits for the patients participating in the study. Non-participation will not affect the patient's care and they will be treated according to the current standard of care employed by the University of Rochester's Rhinology clinic.

Protection Against Risk

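### The primary outcome is change in RSDI score, but the only non-inferiority limit and SD are percentages tied to no scale, so neither the margin nor the stated power can be applied to that outcome as written

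*Combined protocol and SAP*

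**What the plan says.** Study Design names a continuous primary outcome: "Change in Rhinosinusitis Disability Index (RSDI) scores will serve as the primary outcome". It gives the scale as follows: "Total scores range between 0 and 120 with high scores indicating greater burden of disease".

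The sample-size paragraph under Methods, Subjects rests on two assumptions. The first is a responder proportion when treatment finishes: "90% of patients taking culture-directed oral antibiotics will experience a clinical and statistically significant improvement in Rhinosinusitis Disability Index (RSID) score". The second is the limit: "The non-inferiority limit of topical therapy is 20% of oral therapy". The calculation is then given in one sentence: "Using a standard deviation of 20% and a power of 0.9, 26 subjects will be required in each treatment group". Enrolment is set at 35 per group to allow for exclusions and dropout.

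On analysis, Data Collection, Analysis and Monitoring says only: "The results will be analyzed at the study's completion". Molecular Analysis sizes an exploratory transcriptional profiling part from a treatment failure rate ("Numbers of patients for this part of the study will be determined based on the failure of therapy rate"), but failure is not defined there or elsewhere.

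**The concern.** A non-inferiority conclusion needs a margin in the units of the primary outcome and a rule that compares a confidence limit with it. Here the outcome is in RSDI points, the control assumption is a percentage of patients, and the limit and the SD are both given as 20% of something unnamed. The limit has a reference (oral therapy), but the text does not say whether it applies to mean RSDI change or to the proportion who improve, or whether it is absolute or relative. The responder reading also lacks a definition: no RSDI fall is named, and statistical significance does not define improvement in an individual patient.

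Two things are at stake. The plan as written gives no determinate verdict on its own primary outcome, so nothing in it would stop the reading from being settled after the data are known. And the claimed power of 0.9 may not belong to the comparison that is eventually made.

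**Working it through.** **Inputs from the plan.** Oral responder proportion 90%; limit 20%; SD 20%; power 0.9; 26 per group required, 35 enrolled (Methods, Subjects); RSDI range 0–120 (Study Design). Alpha is not stated, so one-sided 0.025 and 0.05 are both tried. z values: 1.960 and 1.645 for alpha, 1.2816 for 90% power.

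**Step 1. Reproduce 26 per group.** For means, with no true difference, n = 2 × (SD/M)² × (z_alpha + 1.2816)².

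- M = 18 (20% × 90), SD 20, one-sided 0.025: 2 × (20/18)² × 3.2416² = 25.94, so 26. This matches.
- M = 20, SD 20: 21.01 (0.025) or 17.13 (0.05). No match.
- M = 18, SD 20, one-sided 0.05: 21.15. No match.
- M = 21.6, SD 24, one-sided 0.025: also 25.94.

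The last line shows that only the ratio M/SD = 0.9 can be recovered. The figure 26 points to 18 rather than 20 if the SD is 20, but it does not identify the scale.

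**Step 2. Responder reading.** A yes/no outcome at 90% has SD √(0.9 × 0.1) = 0.30, that is 30 percentage points, not 20. With 90% in both arms, n = 0.18 × (z_alpha + 1.2816)²/M² and power = Φ(M/√(0.18/n) − z_alpha).

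| Margin | One-sided alpha | n per arm for 90% power | Power at 26 | Power at 35 |
|---|---|---|---|---|
| 20 points | 0.025 | 48 (47.28) | 67% | 80% |
| 18 points | 0.025 | 59 (58.37) | 58% | 71% |
| 20 points | 0.05 | 39 (38.54) | 78% | 87% |
| 18 points | 0.05 | 48 (47.58) | 70% | 81% |

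No cell reaches 0.9.

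**Step 3. Mean-change reading.** With neither M nor SD in RSDI points, the power cannot be checked. If M/SD really is 0.9, the noncentral t gives 96% at 35 per arm and 89% at 26 (one-sided 0.025). If instead M were 6 points with SD 20 points (both assumed), it would be 23.5% at 35 per arm, and 90% power would need 2 × (20/6)² × 3.2416² = 233.5, so 234 per arm.

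**Step 4. Can the reading change the verdict?** This is an illustration only, because the mean change and its SD in RSDI points are assumptions. Take 35 per arm, both arms improving by 30 points, SD 20.

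- Mean change: upper 95% limit = t(0.975, 68) × 20 × √(2/35) = 9.5 points. It passes a fixed 18 and fails 20% of the oral change (0.2 × 30 = 6).
- Responders, 32/35 in each arm: lower limit for topical minus oral is −13.1 percentage points (Wald) or −14.9 (Newcombe). It passes 18.
- With mean 40 and SD 15 the upper limit is 7.2 against 0.2 × 40 = 8, so all the readings pass and the flip is gone.

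**Step 5. Simulation with equal true effects.** 35 per arm, normal changes, 40,000 trials per row, 95% intervals. The responder threshold is set at mean − 1.2816 × SD to give 90% responders.

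| Mean, SD (assumed) | Passes 20% of observed oral mean | Responders pass 18 points (Wald) | Verdicts differ |
|---|---|---|---|
| 30, 20 | 22% | 72% | 53% |
| 30, 15 | 36% | 72% | 41% |
| 40, 20 | 37% | 72% | 41% |
| 40, 15 | 61% | 72% | 28% |

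Part of the disagreement is low power rather than ambiguity: the responder reading alone fails about 28% of these equal-effect trials.

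**The case against.** The best defence is that the plan's own arithmetic narrows the choice. The figure 26 implies a margin/SD ratio of 0.9. If the limit and the SD share one base, identical arms at 35 per arm have an upper limit of about 9.5% of that base, which passes 18% and 20% alike, and the trial is well powered. On this view a limit of 6 RSDI points with SD 20 is the reviewer's construction, since it would call for 234 per arm rather than 26.

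Much of this stands. A reader might infer from Step 4 that the choice between responders and mean change by itself reverses the result. The example does not show that: both pass at 18, and the reversal comes from a relative limit against a fixed one, under assumed inputs. The simulated rates also depend on the method. Using the contrast that matches a relative limit (0.8 × oral minus topical) raises the mean-reading pass rate to about 27% at (30, 20) and about 44% at (30, 15) and (40, 20).

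Two other strong readings also go too far. One is that 26 is an arithmetic error; it reproduces. The other is that the investigators intend to choose the reading afterwards; the documents leave that open but do not say it. The undefined failure rate under Molecular Analysis sizes an exploratory part, not the primary comparison, and carries little weight here.

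The defence does not supply what is missing. A ratio of 0.9 is not a margin in RSDI points, and the 18 that fits SD 20 comes from a proportion of patients. Reading the limit as a responder margin instead conflicts with the named primary outcome, leaves response undefined and misses the stated power.

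**Conclusion.** The concern holds as a gap between the stated primary outcome and the stated margin and power. The absence of an RSDI-point margin and SD, an improvement threshold, an alpha and a decision rule is a matter of text and needs no assumption.

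The firmest number is the responder power: 58–78% at 26 per arm and 71–87% at 35, against 0.9 claimed. It rests on the plan's own 90%, equal true proportions, margins of 18 or 20 percentage points, and the two usual one-sided alphas. On the mean-change reading the documents do not support calling the trial underpowered; they support only that its power cannot be verified, and that it is 96% at 35 per arm if the margin really is 0.9 SD.

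That the verdict can depend on the reading is shown as possible, not as likely. Across the four assumed combinations the readings disagree in 28–53% of equal-effect trials, partly through low power, and the worked example disappears with a smaller SD or a larger change. The point should be fixed before unblinding, because a non-inferiority claim depends on a margin set in advance.

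**What to change.** Keep change in RSDI as primary and write one rule: topical is non-inferior if the upper limit of the two-sided 95% CI for topical minus oral in mean end-of-treatment RSDI, adjusted for baseline RSDI, is below M RSDI points. M should be one fixed number with its justification. State alpha. Replace the sample-size sentence with the power that 35 enrolled and 26 evaluable per arm give for M, using an SD in RSDI points.

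If a responder endpoint is preferred, name it as primary in place of change in score, define the RSDI fall that counts, drop statistical significance from the definition, fix the margin in percentage points, and restate the power as in Step 2.

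The cost is wording, settled before unblinding. Questionnaires are already completed at week 0 and at the end of therapy, and no added enrolment is required. The downside is that the stated power or the achievable margin may look less favourable. Without baseline adjustment, 90% power at one-sided 0.025 needs a margin of about 0.79 SD at 35 per arm and 0.92 SD at 26; baseline adjustment can lower this. If the justified margin is tighter, the plan must state lower power or enrol more patients.
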